## 9.1 ADVERSE EVENTS

AEs will be coded using the *Medical Dictionary for Regulatory Activities*.

An AE (classified by preferred term) that occurs during the OLTP or thereafter will be considered a treatment-emergent adverse event (TEAE) if it was not present before the date of the first dose of IP in the lead-in study or was present before the first dose of IP in the lead-in study and increased in severity during the OLTP or thereafter. An AE that becomes serious during the OLTP or thereafter will also be considered as a TEAE. If more than 1 AE is reported before the date of the first dose of IP in the lead-in study and coded to the same preferred term, the AE with the greatest severity will be used as the benchmark for comparison with the AEs occurring during the OLTP or thereafter that were also coded to that preferred term. An AE that occurs more than 30 days after the date of the last dose of IP will not be counted as a TEAE.

An AE (classified by preferred term) that occurs during the OLTP of the study will be considered a newly emergent adverse event (NEAE) if the AE was not present before the first dose of IP in the OLTP or it was present before the first dose of IP in the OLTP and increased in severity during the OLTP. An AE that becomes serious during the OLTP will also be considered as an NEAE. If more than 1 AE is reported before the first dose of IP in the OLTP and coded to the same preferred term, the AE with the greatest severity will be used as the benchmark for comparison with the AEs occurring during the OLTP that were also coded to that preferred term.

An AE (classified by preferred term) that occurs during the DBTP of the study will be considered an NEAE if the AE was not present before the first dose of IP in the DBTP or it was present before the first dose of IP in the DBTP and increased in severity during the DBTP. An AE that becomes serious during the DBTP will also be considered as an NEAE. If more than 1 AE is reported before the first dose of IP in the DBTP and coded to the same preferred term, the AE with the greatest severity will be used as the benchmark for comparison with the AEs occurring during the DBTP that were also coded to that preferred term.

An AE (classified by preferred term) that occurs during the SFU of the study will be considered an NEAE if the AE was not present before or at Visit 122 or it was present before or at Visit 122 and increased in severity during the SFU. An AE that becomes serious during the SFU will also be considered as an NEAE. If more than 1 AE is reported before or at Visit 122 and coded to the same preferred term, the AE with the greatest severity will be used as the benchmark for comparison with the AEs occurring during the SFU that were also coded to that preferred term.

An AE that occurs more than 30 days after the date of the last dose of IP will not be counted as an NEAE.

The number and percentage of patients reporting TEAEs and NEAEs during the OLTP will be tabulated overall by SOC and preferred term. The number and percentage of patients in each treatment group reporting TEAEs and NEAEs during the DBTP and during the SFU will be tabulated by SOC and preferred term; by SOC, preferred term, and severity; and by SOC, preferred term, and causal relationship to the IP. If more than 1 AE is coded to the same preferred term for the same patient during the same treatment period, the patient will be counted only once for that preferred term using the most severe and most related occurrence for the summarization by severity and by causal relationship to the IP.

[figure not shown]
The incidence of common ( $\geq 2\%$  of patients in any treatment group) TEAEs and NEAEs during the OLTP will be summarized overall by preferred term. Similarly, the incidence of common TEAEs and NEAEs during the DBTP and during the SFU will be summarized by preferred term and treatment group and will be sorted by decreasing frequency starting with the weekly rapastinel group followed by the biweekly rapastinel group.

[figure not shown]
An SAE that occurred between the date of the first dose of IP in the OLTP and 30 days after the date of the last dose of IP, inclusive, will be considered a treatment-emergent SAE (TESAE). The number and percentage of patients who had TESAEs during the OLTP will be summarized overall by preferred term and sorted by decreasing frequency. The number and percentage of patients who had TESAEs during the DBTP and during the SFU will be summarized by treatment group and preferred term and will be sorted by decreasing frequency starting with the weekly rapastinel group followed by the biweekly rapastinel group.

The number and percentage of patients who had fatal TESAEs during the OLTP will be summarized overall by preferred term and sorted by decreasing frequency. The number and percentage of patients who had fatal TESAEs during the DBTP and during the SFU will be summarized by treatment group and preferred term and sorted by decreasing frequency starting with the weekly rapastinel group followed by the biweekly rapastinel group.

The incidence of TEAEs leading to premature discontinuation of IP during the OLTP will be summarized overall by preferred term and will be sorted by decreasing frequency. The incidence of AEs leading to premature discontinuation of IP during the DBTP will be summarized by preferred term and treatment group and will be sorted by decreasing frequency starting with the weekly rapastinel group followed by the biweekly rapastinel group.

[figure not shown]
Listings will be presented for all patients with SAEs, patients with AEs leading to discontinuation, and patients who died (if any).

[figure not shown]

[figure not shown]

[figure not shown]

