## **2.0 INTRODUCTION**

This Statistical Analysis Plan (SAP) describes the methodology that will be used to summarize the statistical analyses of the efficacy and safety data for the final protocol Amendment 2 of Study RAP-MD-04 (version dated 13 Nov 2018).

Study RAP-MD-04 is a multicenter, double-blind, randomized, placebo-controlled, parallel-group study to evaluate the efficacy, safety, and tolerability of rapastinel as long-term maintenance treatment for patients with major depressive disorder (MDD) who completed 1 of the rapastinel lead-in studies (RAP-MD-01, RAP-MD-02, or RAP-MD-03). While the protocol was written to accommodate the potential recruitment of *de novo* patients, there were no *de novo* patients enrolled. Consequently, all analysis in this document pertains specifically to roll-over patients only.

The study will be conducted for the roll-over patients in the following periods:

- An 8- to 16-week, open-label treatment period (OLTP) where patients receive rapastinel 450 mg IV weekly
- A randomized, double-blind treatment period (DBTP) of at least 26 weeks (and up to 104 weeks) where patients are randomized 1:1:1 to either rapastinel 450 mg weekly, rapastinel 450 mg biweekly or placebo
- A 2-week safety follow-up period (for patients who do not enter the RAP-MD-06 extension study only)

In order for patients to transition from the OLTP and be randomized into the DBTP, the patient must meet the stable responder criterion sometime after 8 weeks (and up to 16 weeks) during the OLTP. A patient will be considered a stable responder upon achieving both criteria (1) and (2) below:

- 1) An observed Montgomery-Asberg Depression Rating Scale (MADRS) total score  $\leq 12$  with no more than one modest MADRS excursion (MADRS total score  $> 12$  but  $\leq 16$ ) for at least 6 consecutive weeks.
- 2) An observed MADRS total score  $\leq 12$  for at least 2 consecutive visits prior to randomization.

To meet these criteria a patient must have no missing MADRS assessments within the last 6 consecutive weeks prior to randomization.

The OLTP starts with the first dose of open-label treatment and ends with 1 of the following: the last scheduled assessment at the Visit 122/Early Termination for patients who do not enter the DBTP; the first dose of double-blind treatment for patients who enter the DBTP.

[figure not shown]

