The double-blind treatment period starts when the first dose of double-blind treatment is administered and ends with the last scheduled assessment at Visit 122 (or ET).

[figure not shown]
For patients not entering RAP-MD-06, the safety follow-up (SFU) period starts after completion of the last scheduled assessment at Visit 122 (or ET) and ends with the last available assessment.

[figure not shown]
Individual treatment durations will vary, as patients enrolled early in the study will be allowed to continue treatment in the DBTP until a relapse occurs or the study is terminated. The maximum duration of the study will be 104 weeks (the study ends when all randomized patients have either met relapse criteria, early terminated for other reasons, or completed 26 weeks of the DBTP).

[figure not shown]

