## **7.0 EXTENT OF EXPOSURE AND TREATMENT COMPLIANCE**

### **7.1 EXTENT OF EXPOSURE**

Exposure to open-label rapastinel for the Open-label Safety Population during the OLTP will be summarized for treatment duration, calculated as the number of days from the date of the first dose of open-label rapastinel taken to the date of the last dose taken during the OLTP, inclusive. Descriptive statistics will be presented.

Exposure to double-blind IP for the Double-blind Safety Population during the DBTP will be summarized for treatment duration, calculated as the number of days from the date of the first dose of double-blind IP taken to the date of the last dose taken during the DBTP, inclusive. Descriptive statistics will be presented by treatment group.

The number of IV doses of rapastinel administered to each patient during the OLTP will be summarized using descriptive statistics for the Open-label Safety Population.

Similarly, the number of IV doses administered to each patient during the DBTP will be summarized by treatment group, using descriptive statistics for the Double-Blind Safety Population.

The number and percentage of patients taking each qualifying ADT in the OLTP will be summarized for the Open-label ITT Population; the number and percentage of patients taking each qualifying ADT in the DBTP will be summarized by double-blind treatment group for the Double-Blind mITT Population. Mean daily dose and duration of previous treatment with each qualifying ADT will be summarized using descriptive statistics for the OLTP and by double-blind treatment group for the DBTP for the respective ITT or mITT populations.

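### The visible double-blind AE tables give only crude percentages although relapse ends treatment, so an effective rapastinel arm is expected to show modestly higher percentages for AEs that accrue over time

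*SAP*

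**What the plan says.** SAP section 9.1 defines the main double-blind AE table as "The number and percentage of patients in each treatment group reporting TEAEs and NEAEs during the DBTP", by system organ class and preferred term. Within a treatment period "the patient will be counted only once for that preferred term", however long that patient was observed. For frequent events, "the incidence of common TEAEs and NEAEs during the DBTP and during the SFU will be summarized by preferred term and treatment group". The tables of treatment-emergent SAEs, fatal SAEs and AEs leading to discontinuation follow the same pattern of counts, percentages or incidence by arm. No visible text gives a person-time denominator or a cumulative incidence at a stated time.

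Section 2.0 sets a double-blind period of at least 26 and at most 104 weeks, in which "patients enrolled early in the study will be allowed to continue treatment in the DBTP until a relapse occurs or the study is terminated". Section 9.1 also closes the AE window after dosing stops: "An AE that occurs more than 30 days after the date of the last dose of IP will not be counted as an NEAE".

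Section 7.1 reports exposure separately: "Exposure to double-blind IP for the Double-blind Safety Population during the DBTP will be summarized for treatment duration", by treatment group. It also reports the number of IV doses by arm. No visible AE table uses either.

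**The concern.** The event that ends a patient's time at risk for AEs is the primary efficacy event. If rapastinel prevents relapse as planned, placebo patients leave the double-blind period sooner and have less time in which to report an AE. Randomization does not balance this, because the difference in observation time is itself an effect of treatment.

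A crude percentage then mixes AE risk with time observed. An AE that rapastinel does not influence is expected to look somewhat more frequent on rapastinel, and an AE that rapastinel reduces would have that benefit understated. The percentages also have no common time base, so a reader cannot correct a preferred-term row from the table alone.

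**Working it through.** **Inputs from SAP section 13.0.** Placebo relapse 19% per 26 weeks; dropout 20% per 26 weeks in all arms; hazard ratio 0.475; 200 per group.

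**Assumptions not in the SAP.** Constant hazards; an AE hazard equal in both arms, with 20% risk per 26 weeks; the distribution of potential follow-up, varied below. The 30-day tail after the last dose is ignored.

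**Weekly hazards.**
- Placebo relapse: −ln(0.81)/26 = 0.008105
- Rapastinel relapse: 0.475 × 0.008105 = 0.003850
- Dropout: −ln(0.80)/26 = 0.008582
- Leaving for either reason, k: 0.016687 on placebo, 0.012432 on rapastinel
- AE, r: −ln(0.80)/26 = 0.008582

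**The plan's own figure first.** Expected relapses in 52 weeks are 200 × (relapse hazard/k) × (1 − exp(−52k)), which gives 56.3 on placebo and 29.5 on rapastinel, 85.8 in total. Freedman's formula gives z = √85.8 × (1 − 0.475)/(1 + 0.475) − 1.96 = 3.30 − 1.96 = 1.34, or 90.9% power. This agrees with the stated 90%, so these hazards represent the plan adequately.

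**Exposure and crude percentage.** For potential follow-up T:
- mean exposure = (1 − exp(−kT))/k
- crude AE proportion = r/(r + k) × (1 − exp(−(r + k)T))

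For T = 26, placebo gives 0.3396 × 0.4816 = 16.4% and rapastinel gives 0.4084 × 0.4210 = 17.2%. For uniform follow-up the formulas are averaged over T.

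| Potential follow-up | Mean exposure, weeks (placebo vs rapastinel) | Exposure ratio | Crude AE % (placebo vs rapastinel) | Gap, points |
|---|---|---|---|---|
| All 26 weeks | 21.1 vs 22.2 | 1.05 | 16.4 vs 17.2 | 0.8 |
| Uniform 26–52 | 28.4 vs 30.7 | 1.08 | 21.1 vs 22.6 | about 1.5 |
| All 52 weeks | 34.8 vs 38.3 | 1.10 | 24.8 vs 27.2 | about 2.3 |
| Uniform 26–104 | 38.2 vs 43.2 | 1.13 | 26.3 vs 29.2 | 2.9 |
| All 104 weeks | 49.4 vs 58.4 | 1.18 | 31.5 vs 36.3 | about 4.7 |

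The ratio of crude percentages approaches the exposure ratio as the AE becomes rarer. Across 52-week AE risks of 5% to 70%, the spurious ratio is about 1.05 (26 weeks), 1.08–1.10 (52 weeks), 1.09–1.13 (uniform 26–104) and 1.11–1.18 (104 weeks). The largest gap is about 6 points.

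**First-event rate under the same assumptions.** Dividing patients with a first event by time at risk to that event returns r in both arms: 52 × 0.008582 = 0.446 per 52-week year, or 44.6 per 100 patient-years, ratio 1.00.

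**Early-onset AE, where the rate misleads.** Take an AE possible only in the first 4 weeks, with 30% risk and the same hazard in both arms (assumed): q = −ln(0.70)/4 = 0.0892 per week.
- Crude percentage: q/(q + k) × (1 − exp(−4(q + k))) = 29.1% vs 29.3%, ratio 1.01.
- Mean time at risk to first event: (1 − exp(−4(q + k)))/(q + k) + exp(−4(q + k)) × (1 − exp(−k(T − 4)))/k. This gives 15.3 vs 16.1 weeks for T = 26, and 27.3 vs 30.8 weeks for uniform 26–104.
- Rate ratio, rapastinel to placebo: 1.01 × 15.3/16.1 = 0.96, and 1.01 × 27.3/30.8 = 0.89. Uniform 26–52 and all 52 weeks give 0.94 and 0.92.

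**The case against.** **Parts of section 9 are not shown.** An exposure-adjusted table could stand there. This stands as a limit: the point concerns the tables as visibly specified, and the request falls away if such a table exists.

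**The bias is small against sampling error.** With 200 per arm, the standard error of the difference in percentages is about 3.7 points (26 weeks), 4.1 (uniform 26–52) and 4.5 (uniform 26–104). The expected gaps of 0.8, 1.5 and 2.9 points are about 0.2, 0.4 and 0.65 of a standard error. A reader might infer that an effective arm will show more AEs than placebo; the figures support only a shift in expectation.

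**Varying follow-up is not itself a cause.** A reader might infer that the 26-to-104-week range biases the comparison. Randomization balances planned follow-up across arms. The bias comes from stopping at relapse, and longer follow-up enlarges it.

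**The tables are descriptive and conventional, and exposure is reported by arm.** This is fair: section 9.1 visibly specifies no AE test, difference or ratio, and section 7.1 lets a reader see an exposure imbalance. It does not let the reader correct a preferred-term row. A reader might also conclude that the study's only randomized safety comparison is compromised. That goes too far, because section 15.4 refers to other safety parameters whose analysis text is not visible.

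**An exposure-adjusted rate has its own bias.** This stands in full. For early-onset AEs the crude percentage is nearly unbiased, while the rate favours rapastinel by 4% to 11%. The rate cannot simply replace the percentage.

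**Conclusion.** The concern holds in a limited form. For AEs that accrue over time, stopping at relapse is expected to raise the crude percentage on an effective rapastinel arm even when the AE hazard is identical. At an assumed 20% AE risk per 26 weeks, the excess is 0.8 to 2.9 points (5% to 11% relative) for follow-up from 26 weeks to uniform 26–104 weeks. For rarer AEs the relative excess reaches 13%, or about 18% if everyone were followed for 104 weeks. It is negligible for AEs confined to the first weeks.

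The size rests on the SAP's planning rates, constant hazards, and assumed AE risks and follow-up distributions. If rapastinel does not reduce relapse, this bias disappears. The crude tables are not wrong as descriptions; they lack a companion measure that accounts for time, in a design that plans for unequal observation.

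**What to change.** Unless a part of section 9 that is not shown already does so, add to section 9.1, by arm and for double-blind TEAEs, NEAEs, treatment-emergent SAEs and AEs leading to discontinuation, one or both of:

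- patients with a first event per 100 patient-years at risk, with time stopped at the first event or the end of the AE window, and a 95% CI;
- cumulative incidence at fixed times, for example 26 and 52 weeks.

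Keep the crude percentages beside them. State that the measures are read together and that the rate is not the sole basis for comparing arms, because it assumes a roughly constant hazard and can understate early-onset AEs on rapastinel.

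The cost is a little more programming and the constant-hazard caveat. The dose and AE dates are already needed for sections 7.1 and 9.1.

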**RESTRICTED**

*RESTRIC*

**11.0**

**INVESTIGATIONAL PRODUCT PLASMA CONCENTRATION  
PARAMETERS**

Analyses of plasma concentrations of rapastinel will be summarized in a separate document governing the PK analysis.

**RESTRICTED**

**12.0** **INTERIM ANALYSIS**

No interim analysis is planned for this study.

RESTRUCTURED

**13.0**

**DETERMINATION OF SAMPLE SIZE**

The sample size and power calculations are based on the analysis of time to relapse during the first 52 weeks of the DBTP. Assuming a relapse rate of 19% per 26 weeks in the placebo group and a dropout rate of 20% per 26 weeks in all treatment groups, the sample size of 200 per group will have 90% power to detect a hazard ratio of 0.475 for a rapastinel treatment versus placebo at a 0.05 significance level. To achieve this number of randomized patients, approximately 1500 patients need to be enrolled in this study if 40% of patients are qualified for randomization.

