## **8.1 PRIMARY EFFICACY ANALYSIS**

The primary efficacy parameter is the time to first relapse. Relapse during the DBTP is defined as meeting any of the following criteria:

- MADRS total score  $\geq 18$  at 2 consecutive assessments. The 2 MADRS assessments must occur on different calendar dates
- $\geq 2$  increase in CGI-S score compared with that obtained at randomization
- Risk of suicide as determined by the investigator
- Need for hospitalization due to worsening of depression as determined by the investigator
- Need for alternative treatment of depressive symptoms as determined by the investigator

Further details on the derivation of the relapse criterion are provided in section 15.3.

The primary endpoint is the time to first relapse during the first 52 weeks of the DBTP, defined as relapse date – randomization date + 1. Patients who do not meet the above relapse criteria during the first 52 weeks of the DBTP will be censored at 52 weeks or the time of completion or discontinuation from the study, whichever is earlier.

The primary efficacy analysis is to evaluate the time to first relapse in MDD patients who are stable responders to open-label treatment with rapastinel for MDD.

The primary null hypothesis is that the distribution of the time to first relapse for each of the rapastinel 450 mg weekly and 450 mg biweekly treatment groups is not different from that for the placebo treatment group. The primary alternative hypothesis is that the distribution of the time to first relapse for either of the rapastinel 450 mg weekly and 450 mg biweekly treatment groups is different from that for the placebo treatment group.

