## 8.2 SECONDARY EFFICACY ANALYSIS

The secondary efficacy endpoint is the time to first relapse during the entire DBTP, defined as the number of days from the randomization date to the relapse date during the entire DBTP. For patients who did not meet the relapse criteria during the DBTP, their time to relapse will be censored at the time of completion or discontinuation from the study. The same analysis method for the primary endpoint will be applied to the secondary endpoint.

In order to control the overall Type I error rate for the primary and secondary hypotheses, the following sequential testing procedure will be implemented in the following order:

- 1) The comparison of time to relapse during the first 52 weeks between rapastinel 450 mg weekly and placebo
- 2) The comparison of time to relapse during the entire DBTP between rapastinel 450 mg weekly and placebo
- 3) The comparison of time to relapse during the first 52 weeks between rapastinel 450 mg biweekly and placebo
- 4) The comparison of time to relapse during the entire DBTP between rapastinel 450 mg biweekly and placebo

Each of the 4 hypothesis tests above will be implemented at the 2-sided 0.05 significance level. A given hypothesis test will be carried out only when each of the preceding hypothesis tests have concluded rejection of the null hypothesis at the 0.05 significance level. In the event a given hypothesis test fails to reject its null hypothesis at the 0.05 significance level, the conclusion for the subsequent hypotheses not tested is to not reject their respective null hypotheses. This testing strategy will control the overall Type I error rate at 0.05 significance level.

*REDACTED*

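### Does the 90% power in SAP Section 13 overstate the power for the biweekly arm, which is tested third in the Section 8.2 sequence?

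*SAP*

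**What the plan says.** Section 13 bases the calculation on the first 52 weeks of the double-blind period: "The sample size and power calculations are based on the analysis of time to relapse during the first 52 weeks of the DBTP". Its input for relapse is "Assuming a relapse rate of 19% per 26 weeks in the placebo group". For withdrawals it takes "a dropout rate of 20% per 26 weeks in all treatment groups". Its result, with the test level set at 0.05, is that "the sample size of 200 per group will have 90% power to detect a hazard ratio of 0.475 for a rapastinel treatment versus placebo". It names neither regimen and does not refer to the testing order.

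Section 8.2 sets a fixed sequence of four tests: weekly at 52 weeks, weekly over the entire double-blind period, biweekly at 52 weeks, biweekly over the entire period. On the level it says "Each of the 4 hypothesis tests above will be implemented at the 2-sided 0.05 significance level", and on the gate "A given hypothesis test will be carried out only when each of the preceding hypothesis tests have concluded rejection of the null hypothesis". Third in the list is "The comparison of time to relapse during the first 52 weeks between rapastinel 450 mg biweekly and placebo".

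Section 8.1 words the primary alternative, relative to placebo, so that one effective regimen is enough: "the distribution of the time to first relapse for either of the rapastinel 450 mg weekly and 450 mg biweekly treatment groups is different".

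**The concern.** Both regimens belong to the primary objective, so the biweekly 52-week comparison is a primary comparison. Section 13 speaks of a rapastinel treatment without saying which, and a reader could apply the 90% to either. Under Section 8.2 the biweekly test is reached only if both weekly tests reject, so its chance of success cannot exceed its stand-alone power and is normally lower. If the design effect holds in both arms, the risk of missing it in the biweekly arm is about 17% rather than 10%. That would matter to anyone judging how informative a failed or untested biweekly comparison is.

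**Working it through.** **Inputs.** From Section 13: 200 per group, HR 0.475, placebo relapse 19% per 26 weeks, dropout 20% per 26 weeks, 52-week window. From Section 8.2: two-sided 0.05 for each test. From Section 2.0: 1:1:1 allocation and a double-blind period of 26 to 104 weeks. The SAP does not give the distribution of follow-up, so it is assumed below.

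**Step 1: reproduce the 90%.** With exponential times, the weekly hazards are:

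- placebo relapse: −ln(0.81)/26 = 0.00810
- rapastinel relapse: 0.475 × 0.00810 = 0.00385
- dropout: −ln(0.80)/26 = 0.00858

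Expected events per arm are 200 × λ/(λ+d) × [1 − exp(−(λ+d)T)]. At T = 52 this gives 56.3 (placebo) and 29.5 (rapastinel), 85.8 in total.

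The Schoenfeld requirement for 90% power is 4 × (1.960 + 1.282)² / (ln 0.475)² = 75.8 events. Power with 85.8 events is Φ(√(85.8/4) × |ln 0.475| − 1.960) = 93.2%; Freedman's formula gives 91.0%.

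If follow-up is uniform over 26–104 weeks, cut at 52, there are 80.4 events and power is 91.6% (Schoenfeld) or 89.1% (Freedman). Uniform over 26–78 weeks gives 77.8 events and 90.7% or 88.1%. The stated 90% is sound as the power of one comparison.

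**Step 2: apply the sequence.** Give each of tests 1 and 3 a mean of 1.960 + 1.282 = 3.242, so that each alone has 90% power. The chance that both reject is the bivariate normal probability Φ₂(1.282, 1.282; ρ). A shared placebo arm with equal allocation gives ρ of about 0.5.

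| ρ | Both reject |
|---|---|
| 0 | 81.0% |
| 0.4 | 82.7% |
| 0.5 | 83.2% |
| 0.6 | 83.9% |

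At ρ = 0.5 the shortfall is 90.0 − 83.2 = 6.8 points. Starting from the 93.2% of full 52-week follow-up, the joint figure is 88.2%, a shortfall of 5.0 points.

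**Step 3: add the gate at test 2.** Log-rank simulation of three arms (8000 trials per row, HR 0.475 in both rapastinel arms):

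| Assumed follow-up | Test 1 alone | Test 3 alone | Tests 1 and 3 | Tests 1 to 3 |
|---|---|---|---|---|
| All 52 weeks | 91.7% | 91.9% | 86.2% | 86.2% |
| Uniform 26–104 weeks | 90.5% | 90.6% | 84.3% | 83.8% |
| Uniform 26–78 weeks | 89.5% | 89.2% | 82.5% | 81.8% |

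The gate at test 2 costs at most about 0.7 points, because the two weekly tests are highly correlated. Shorter follow-up lowers everything together: uniform 26–52 weeks gives about 86% per comparison and 77% through test 3. That case no longer matches the 90% in Section 13, so it says nothing specific about the sequence.

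**Step 4: vary the weekly effect.** Hold biweekly at HR 0.475 (90% alone, ρ = 0.5) and scale the weekly mean by ln(HR)/ln(0.475). The weekly hazard ratios other than 0.475 are illustrative.

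| Weekly HR | Biweekly power (tests 1 and 3) |
|---|---|
| 0.35 | 89.8% |
| 0.40 | 88.9% |
| 0.45 | 85.9% |
| 0.50 | 79.7% |
| 0.55 | 70.0% |
| 0.60 | 58.0% |

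If weekly is clearly the stronger regimen, the loss nearly vanishes.

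**Step 5: compare with the wording.** In a fixed sequence, rejection for at least one arm requires test 1 to reject. The power to reject for at least one arm is therefore the power of test 1, the 90% that Section 13 states.

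**The case for a change.** The best argument for a change is that biweekly at 52 weeks is a primary comparison and the SAP gives no power for it under the rule that decides it. The wording in Section 13 covers either regimen, while the sequence delivers the full figure for only one of them. The shortfall is real, it is reproduced by formula and by simulation, and one sentence would disclose it.

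The arithmetic stands, and so does the observation that Section 13 is silent on the sequence. The claim of a conflict does not. A per-comparison power and a gatekeeping rule can both be true, and Section 13 claims neither joint power nor gated power for the biweekly arm. Section 8.2 sets out the order and the gate explicitly, and anyone interpreting the biweekly result has to use it. Quoting per-comparison power beside a fixed sequence is ordinary practice. A flat 83% would also need its own caveats: it holds only if per-comparison power is exactly 90% and the hazard ratios are equal, and it leaves out the gate at test 2.

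**Conclusion.** No change is needed. The 90% is a correct per-comparison power. It applies in full to weekly versus placebo at 52 weeks, and it matches the primary alternative, which needs only one regimen to differ. With HR 0.475 in both arms, the biweekly 52-week comparison has about 82% to 88% power within the sequence, depending on the follow-up assumed and on whether a formula or simulation is used; it is about 83% if per-comparison power is exactly 90%. This rests on exponential relapse and dropout at the Section 13 rates, a correlation near 0.5 from the shared placebo arm, and follow-up that keeps per-comparison power near 90%. Lower power for a later test is the accepted price of testing every step at the full 0.05 level. Stating it would help a careful reader a little, but type I error control, sample size, testing order, analyses and conclusions would all stay as they are.
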